### **9.13 Post-trial IMP arrangements**

There is no plan to allow continued treatment with ketamine.

## 10 Recording and reporting of adverse events and reactions

### 10.1 Definitions

Term	Definition
Adverse Event (AE)	Any untoward medical occurrence in a patient or clinical trial subject administered a medicinal product and which does not necessarily have a causal relationship with this treatment.
Adverse Reaction (AR)	Any untoward and unintended response in a subject to an investigational medicinal product which is related to any dose administered to that subject. This includes medication errors, uses outside of protocol (including misuse and abuse of product)
Serious adverse event (SAE), serious adverse reaction (SAR) or unexpected serious adverse reaction	Any adverse event, adverse reaction or unexpected adverse reaction, respectively, that: 
 
• results in death,
 
• is life-threatening,
 
• requires hospitalisation or prolongation of existing hospitalisation,
 
• results in persistent or significant disability or incapacity, or
 
• consists of a congenital anomaly or birth defect
 

Important Medical Event	These events may jeopardise the subject or may require an intervention to prevent one of the above characteristics/consequences. Such events should also be considered 'serious'.
Unexpected adverse reaction	An adverse reaction the nature and severity of which is not consistent with the information about the medicinal product in question set out: 
 
(a) in the case of a product with a marketing authorization, in the summary of product characteristics for that product,
 
(b) in the case of any other investigational medicinal product, in the investigator's brochure relating to the trial in question.
 

SUSAR	Suspected Unexpected Serious Adverse Reaction

### 10.2 Recording adverse events

All adverse events will be recorded in the medical records and CRF only following consent.

If the investigator suspects that the subjects' disease has progressed faster due to the administration of the IMP, then he will record and report

this as an unexpected adverse event. Adverse events that are known to the IMP when used in its licensed indication (listed in Appendix C, or events that are disease related or related to procedures as listed in section 10.3.3) will only be recorded in the medical notes, however serious AEs will be recorded in the CRF and SAE log.

Clinically significant abnormalities in the results of objective tests (e.g. liver function, biochemistry) will also be recorded as adverse events. If the results are not expected as part of disease or IMP, these will also be recorded as unexpected. All adverse events will be recorded with clinical symptoms and accompanied with a simple, brief description of the event, including dates as appropriate. All adverse events will be recorded until 6 months post-treatment. All Serious Adverse Events will be reportable to the Sponsor from IMP administration up to 30 days post last IMP administration.

### 10.3 Assessments of Adverse Events

Each adverse event will be assessed for the following criteria:

#### 10.3.1 Severity

Category	Definition
Mild	The adverse event does not interfere with the volunteer's daily routine, and does not require intervention; it causes slight discomfort.
Moderate	The adverse event interferes with some aspects of the volunteer's routine, or requires intervention, but is not damaging to health; it causes moderate discomfort.
Severe	The adverse event results in alteration, discomfort or disability which is clearly damaging to health.

#### 10.3.2 Causality

The assessment of relationship of adverse events to the administration of IMP is a clinical decision based on all available information at the time of the completion of the case report form. The following categories will be used to define the causality of the adverse event:

Category	Definition
Definitely	There is clear evidence to suggest a causal relationship, and other possible contributing factors can be ruled out.
Probably	There is evidence to suggest a causal relationship, and the influence of other factors is unlikely.
Possibly	There is some evidence to suggest a causal relationship (e.g. the event occurred within a reasonable time after administration of the trial medication). However, the influence of other factors may have contributed to the event (e.g. the patient's clinical condition, other concomitant events).
Unlikely	There is little evidence to suggest there is a causal relationship (e.g. the event did not occur within a reasonable time after administration of the trial medication). There is another reasonable explanation for the event (e.g. the patient's clinical condition, other concomitant treatments).
Not related	There is no evidence of any causal relationship.

Not Assessable	Unable to assess on information available.
----------------	--

### 10.3.3 **Expectedness**

Category	Definition
Expected	An adverse event that is consistent with the information about the IMP listed in the SPC or clearly defined in this protocol.
Unexpected	An adverse event that is classed in nature as serious and which is not consistent with the information about the IMP listed in the SPC.

The reference document to be used to assess expectedness against the IMP and placebo is the SPC. The protocol and SCRAM-X bracelet brochure will be used as the reference document to assess disease related and/or procedural expected events.

The following Adverse Events are expected disease related and/or procedural expected events:

- Bruising caused by venepuncture
- Dissociative and psychotomimetic effects, analgesia, dizziness, lack of co-ordination, unsteadiness, impaired memory and impaired concentration following ketamine infusion
- Skin rash caused by the SCRAM-X bracelet
- Drinking relapse

### 10.3.4 **Seriousness**

Seriousness as defined for an SAE in section 10.1.

Collection, recording and reporting of adverse events (including serious and non-serious events and reactions) to the sponsor will be completed according to the sponsor's SOP (INV/S05).

## 10.4 **Procedures for recording and reporting Serious Adverse Events**

All serious adverse events will be recorded in the hospital medical notes and the CRF, and the sponsor's AE log. The AE log will be reported to the sponsor at least once per year. The Chief or Principal Investigator will complete the sponsor's serious adverse event form and the form will be faxed to the sponsor on [name] or preferably emailed on [contact], within 24 hours of his / her becoming aware of the event. The Chief or Principal Investigator will respond to any SAE queries raised by the sponsor as soon as possible. All SUSARs must be notified to the

sponsor immediately (within 24 hours) according to the sponsor's written SOP. Reporting to the sponsor will be completed as per the sponsor's SOP and using the UCL SAE form (INV/S05).

## **10.5 Notification of deaths**

All deaths, including deaths deemed unrelated to the IMP, if they occur earlier than expected will be reported to the sponsor within 24 hours of site being made aware of the event.

### **10.5.1 Reporting SUSARs**

The sponsor will notify the main REC and MHRA of all SUSARs. SUSARs that are fatal or life-threatening must be notified to the MHRA and REC within 7 days after the sponsor has learned of them. Other SUSARs must be reported to the REC and MHRA within 15 days after the sponsor has learned of them. The procedure for unblinding in the event of a SUSAR is documented in section 7.3.

### **10.5.2 Development Safety Update Reports**

The sponsor will provide the main REC and the MHRA with Development Safety Update Reports (DSUR) which will be written in conjunction with the trial team and the Sponsor's office. The report will be submitted within 60 days of the Developmental International Birth Date (DIBD) of the trial each year until the trial is declared ended. This will be done in accordance with the sponsor's SOP (SPON/S17).

### **10.5.3 Annual progress reports**

An annual progress report (APR) will be submitted to the REC within 30 days of the anniversary date on which the favourable opinion was given, and annually until the trial is declared ended. The chief investigator will prepare the APR.

### **10.5.4 Pregnancy (If applicable)**

We intend to record and notify pregnancies to the sponsor (using the sponsor's SOP). Any pregnancy that occurs during the treatment weeks will result in exclusion from treatment.

In the event of a pregnancy occurring during the study, this must be reported using a sponsor pregnancy reporting form.

To ensure subject's safety, each pregnancy must be reported to the sponsor within 24 hours of learning of its occurrence. The pregnancy must be followed to determine the outcome (including premature termination) and status of mother and child.

Pregnancy complications and elective terminations for medical reasons must be reported as an AE or SAE. Spontaneous abortion must be reported as an SAE to the CI and Sponsor within 24 hours of learning of its occurrence.

Any SAE occurring in association with a pregnancy brought to the investigator's attention after the subject has completed the study and considered by the investigator as possibly related to the investigational product, must be promptly reported to sponsor.

#### **10.5.5 Overdose**

We do not envisage an overdose as drugs are prepared by pharmacy and then administered by the anaesthetist at the Clinical Research Facility. Accidental administration of 50 times the protocol dose constitutes an overdose. In the event of an overdose and protocol deviation then the sponsor will be notified (and this information will be placed in the deviation log) and trust policy on incident reporting will be followed. Overdoses will be observed from drug charts, or an anaesthetic response in the patient. If an SAE is associated with the overdose then this will be fully described in the SAE report form. We will use intention to treat analysis in the case of an overdose. In the case of an overdose, the patient will be withdrawn from treatment and will be invited to attend follow up visits 9 and 10 as part of our intention to treat protocol.

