### **7.11.1 Discontinuation from treatment**

The investigator may discontinue a patient from treatment if it is considered necessary for any reason including:

- Ineligibility (either arising during the study or retrospective)
- Significant protocol deviation e.g. if treatment is stopped for longer than 21 days (All protocol deviations and violations will be recorded and reported to the sponsor)
- Significant non-compliance with treatment or study requirements e.g. If the participant misses 2 consecutive infusions, as detailed in section 9.12
- An adverse event which requires discontinuation of the study medication or results in inability to continue to comply with study procedures
- Disease progression which requires discontinuation of the study medication
- Pregnancy
- In the case of an overdose (see section 10.5.5)

Where treatment is discontinued, participants will be invited to attend follow up visits 9 & 10 on the basis of our planned intention to treat analysis which assumes (and formally tests: see section 13.3.4) that data are missing at random.

The reason for participant treatment discontinuation will be recorded in the case report form (CRF).

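### Protocol 10.5.5 sets the overdose threshold at 50 times the dose (40 mg/kg), so fivefold or tenfold errors do not trigger its automatic stop on further infusions

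*Protocol*

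**What the plan says.** Protocol section 10.5.5 defines the event: "Accidental administration of 50 times the protocol dose constitutes an overdose". It then says how such an event would be noticed: "Overdoses will be observed from drug charts, or an anaesthetic response in the patient". Two consequences follow. One is reporting: "In the event of an overdose and protocol deviation then the sponsor will be notified", with an entry in the deviation log and trust incident reporting. The other is a mandatory stop: "In the case of an overdose, the patient will be withdrawn from treatment", with an invitation to follow-up visits 9 and 10. Neither the protocol nor the SAP gives a lower overdose threshold.

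Other sections bear on the same event. Section 7.11.1 gives a discretionary power, "The investigator may discontinue a patient from treatment if it is considered necessary for any reason including" a list of examples, one of which is overdose with a cross-reference to 10.5.5. The same section says: "All protocol deviations and violations will be recorded and reported to the sponsor". Section 9.11 requires withdrawal from study drug if side effects are intolerable. The adverse reaction definition in 10.1 covers medication errors.

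**The concern.** A threshold that switches on a mandatory safety action should lie where errors can plausibly occur and where harm begins to be a worry. Fifty times the dose lies far above both. The risk assessment in section 2.5 leans on the low dose and slow infusion; for example, it sets aside respiratory depression and apnoea because they belong to large doses and rapid infusions. A fivefold or tenfold error weakens that reassurance. Yet, read literally, it would not count as an overdose, and the participant would not automatically be stopped from receiving the next infusion. Safety and tolerability form a primary objective (section 3), so how dosing errors are classified also matters for what is reported.

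**Working it through.** **1. The threshold in mg/kg.** Inputs: dose 0.8 mg/kg over 40 minutes (9.6); multiple 50 (10.5.5). 50 × 0.8 = 40 mg/kg, and 40 / 40 minutes = 1 mg/kg per minute. The protocol gives no mg/kg value, source or derivation for the 50, so there is no planned figure to reproduce.

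**2. Against the protocol's anaesthetic range.** Section 2.4 gives 1 to 4.5 mg/kg over 60 seconds.
- Threshold relative to the top: 40 / 4.5 = 8.9. Relative to the bottom: 40 / 1 = 40.
- The range as multiples of the trial dose: 1 / 0.8 = 1.25 to 4.5 / 0.8 = 5.6.

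These compare total mg/kg only; the rates of administration differ (step 5).

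**3. Smaller errors.**
- Fivefold: 5 × 0.8 = 4 mg/kg, which is 4 / 40 = 10% of the threshold.
- Tenfold: 10 × 0.8 = 8 mg/kg, which is 8 / 40 = 20% of the threshold and 8 / 4.5 = 1.8 times the top of the anaesthetic range.

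Section 9.1 permits vials of 10 mg/ml and 50 mg/ml. For an assumed 70 kg participant the dose is 0.8 × 70 = 56 mg, or 5.6 ml of the weaker product. The same 5.6 ml of the stronger product is 280 mg, and 280 / 70 = 4 mg/kg: a fivefold error.

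**4. What the planned volume can hold.** The infusion is made up to 50 ml (7.6).
- Undiluted 50 mg/ml: 50 × 50 = 2,500 mg. This equals 40 mg/kg at 2,500 / 40 = 62.5 kg and falls short above that weight. At 70 kg the maximum is 2,500 / 56 = 44.6 times the dose. Over assumed weights of 50 to 90 kg the maximum runs from 2,500 / 40 = 62.5 times to 2,500 / 72 = 34.7 times.
- Undiluted 10 mg/ml: 50 × 10 = 500 mg. At 70 kg the maximum is 500 / 56 = 8.9 times the dose. Reaching 40 mg/kg would need a body weight of 500 / 40 = 12.5 kg or less, so no adult could receive the defined overdose.

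**5. Allowing for the slow infusion (illustration only).** Assume one compartment, a constant 40-minute infusion, and the 10 to 15 minute distribution half-life from section 2.2 as the only route of loss. The fraction of the total dose present at 40 minutes is (1 − exp(−40k)) / (40k), with k = ln 2 / half-life. This is 0.338 for 10 minutes and 0.456 for 15 minutes.

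| Multiple | Total mg/kg | Present at 40 minutes, mg/kg |
|---|---|---|
| 1 | 0.8 | 0.27 to 0.36 |
| 5 | 4 | 1.35 to 1.82 |
| 10 | 8 | 2.71 to 3.65 |
| 50 | 40 | 13.5 to 18.2 |

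On this model 1 mg/kg is reached at about 2.7 to 3.7 times the protocol dose and 4.5 mg/kg at about 12.3 to 16.6 times. The model ignores return from tissue and sets an amount remaining against a dose given over 60 seconds. It shows only that adjusting for rate does not bring the anaesthetic range up to 50-fold.

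**6. Which rules apply at five or ten times the dose.** The mandatory stop in 10.5.5: no. Overdose classification: no. Reporting to the sponsor as a deviation (7.11.1): yes. Discretionary discontinuation (7.11.1): yes. Mandatory withdrawal under 9.11: only if side effects are intolerable.

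**The case against.** The best defence is that the practical gap is narrow. An anaesthetist gives the drug with resuscitative equipment at hand (2.5), and vital signs are monitored throughout the infusion (7.6, 7.7, 7.9.1). Deviations go to the sponsor, adverse reactions are followed to resolution or stabilisation (10.6), and serious adverse event and serious breach reporting do not depend on the overdose definition (10.4, 10.6.1). The investigator may stop treatment for any reason. Section 2.5 also reports accidental anaesthetic overdoses of up to ten times the required dose with complete recovery. All of this stands, and it limits the seriousness of the point. It does not justify the number 50, and section 2.5 itself uses the word overdose without any 50-fold test.

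The error scenarios have limits too. Nothing shows that a site holds both vial strengths. A tenfold error with 10 mg/ml vials would not fit in 50 ml above 500 / 8 = 62.5 kg.

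A reader might infer four stronger things that the documents do not support:
- That 10.5.5 contradicts itself. The anaesthetic response is a prompt for detection, not a second definition, and a 50-fold dose would produce it too. The threshold and the sign are badly matched, which is a weaker statement. Drug charts, the other route, work at any multiple.
- That anaesthesia is known to begin at about three times the dose. That comes from the assumed model in step 5; no section gives the multiple over 40 minutes.
- That 7.11.1 and 10.5.5 conflict because one is permissive and the other mandatory. Section 7.11.1 refers to 10.5.5, so the specific rule can govern. Its list also contains pregnancy and two missed infusions, which 10.5.4 and 9.12 make mandatory.
- That the statement "We do not envisage an overdose as drugs are prepared by pharmacy" undermines the threshold. Section 9.7 also allows delegated ward staff to prepare doses, so the statement is incomplete, but that is an editorial matter.

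**Conclusion.** The point holds and should be fixed. The only overdose definition is 40 mg/kg, 8.9 times the top of the protocol's anaesthetic range in total mg/kg. The planned volume cannot deliver it above 62.5 kg with the stronger vial, or to any adult with the weaker one, so the mandatory withdrawal rule would almost never operate. What is missing for a fivefold or tenfold error is the automatic stop on later infusions and classification as an overdose.

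It would be wrong to conclude that smaller errors go unreported or unmanaged. Trust incident reporting is less certain: the phrase pairing overdose with protocol deviation could be read to cover smaller errors, and the trust policy is not among the documents.

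The 40 mg/kg and the syringe limits are plain arithmetic; the 70 kg and 50 to 90 kg weights are assumptions. That an anaesthetic response would come well below 50-fold is a reasonable expectation, but the exact multiple is not known from the documents. The 50 may be a slip for another figure; the documents do not show this. Sample size and the efficacy analysis are not affected by the present wording.

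**What to change.** Delete the 50-fold figure from 10.5.5 and separate the two purposes of the definition.

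- For recording, sponsor notification and trust incident reporting: define overdose as any accidental dose above the protocol dose beyond a stated preparation tolerance.
- For stopping treatment: require withdrawal from further infusions when a confirmed dosing error reaches a clinician-set multiple below five, so that a vial-strength error is caught, or when a confirmed dosing error is accompanied by an anaesthetic response. The exact multiple is a clinical judgement.

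The second trigger should be tied to a confirmed error. Section 2.3 reports three participants who became unresponsive to verbal stimuli in a review of 450 infusions, at doses that section 2.5 calls similar to the trial's. A rule based on the response alone could therefore withdraw correctly dosed participants.

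The cost is a short amendment and a few more events classed as overdoses. Possibly a few more ketamine participants would fall outside the per-protocol set, because SAP section 4.5 requires three infusions of ketamine participants but counts every placebo participant as treated per protocol. The intention-to-treat analysis does not change. The wording about pharmacy preparation can be tidied in the same amendment.

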#### **10.5.6 Reporting Urgent Safety Measures**

If any urgent safety measures are taken the PI/Sponsor shall immediately and in any event no later than 3 days from the date the measures are taken, give written notice to the MHRA and the relevant REC of the measures taken and the circumstances giving rise to those measures. The guidance on the MHRA website will be used for details on clinical trials safety reporting.

#### **10.6 The type and duration of the follow-up of subjects after adverse events.**

If a patient has an adverse reaction during infusion they will be monitored in the Clinical Research Facility until a resolution or stabilisation is reached. If an SAE happens while the subject is not in the research facility they will be given the number of an on-call anaesthetist and told to present to A&E at site (preferably) or the nearest hospital. Any SUSAR related to the IMP will need to be reported to the Sponsor irrespective of how long after IMP administration the reaction has occurred.

### **10.6.1 Notification of Serious Breaches to GCP and/or the protocol (SPON/S15)**

A “serious breach” is a breach which is likely to effect to a significant degree:

- (a) the safety or physical or mental integrity of the subjects of the trial;
- or
- (b) the scientific value of the trial.

The sponsor of a clinical trial shall notify the licensing authority in writing of any serious breach of:

- (a) the conditions and principles of GCP in connection with that trial;
- or
- (b) the protocol relating to that trial, as amended from time to time, within 7 days of becoming aware of that breach.

The sponsor will be notified immediately of any case where the above definition applies during the trial conduct phase. The sponsor’s SOP on the ‘Notification of violations, urgent safety measures and serious breaches’ will be followed.

## **11 Data management and quality assurance**

### **11.1 Confidentiality**

All data will be handled in accordance with the UK Data Protection Act 1998. The Case Report Forms (CRFs) will not bear the subject’s name or other personal identifiable data. The subject’s initials, date of birth and patient ID, will be used for identification.

### **11.2 Data collection tools and source document identification**

Data to be collected can be found in sections 7.5 and 7.7. Every effort will be made to maximise completeness of data. Trial data will be collected in an Electronic Case Report Form hosted on sealedenvelope.com, prepared using their “Red Pill” service ([www.sealedenvelope.com/redpill](http://www.sealedenvelope.com/redpill)). Source data documents will be defined at site prior to the start of the trial.

Full details of source data and documentation will be identified in a separate source document identification list but in summary will comprise of the following:

- Patient Clinical Record (medical notes)
- Trial specific source data worksheets and trial specific logs

- Laboratory test print outs
- Questionnaires and measurement scales
- Encrypted memory stick containing computer tasks data files and SCRAM-X data

Data to be recorded in the source data first and then transcribed into the CRF:

- Patient demographics; age, date of birth and initials
- Medical history including drug use, alcohol use, smoking
- Physical examination
- Patient eligibility assessment
- Allergies
- Concomitant medication
- Study IMP treatment
- Therapies: Psychoeducation Therapy, Relapse-prevention based CBT
- Clinical Assessment measurements: Vital signs, Blood and urine screen. On infusion visits (visits 2, 4 and 6) continuous monitoring of vital signs will occur through the infusion until the participant has recovered. This monitoring will be recorded on a standard observation chart and will be stored as source data. The eCRF will record 3 sets of readings, one prior to the infusion, another after the infusion terminates, and then finally after the participants recovery.
- Adverse Events (refer to section 10)
- Assessment tools:
  - Pattern Recognition Test
  - Stop Signal Reaction Time
  - Delay Discounting (monetary choice questionnaire)
  - Working Memory (digit span WAIS-IV)
  - Prose Recall
  - SCRAM-X checks
  - BPRS
  - PSI
  - Adverse events VAS
  - Craving VAS
  - Fagerstrom smoking
  - Timeline follow Back
  - Drink diary
  - Reasons for drinking questionnaire
  - Columbia Suicide Severity Rating Scale
  - BDI
  - HAM-D
  - POMS

- STAI
- SF-12
- ACQ-NOW

The following data to be collected in the source documents but will not be collected in the CRF:

- Adverse events that are expected for the IMP and which are not serious and listed in section 10

Questionnaires and measurements scales to determine adverse effects/treatment adherence will be delivered in clinics by fully trained staff to ensure completeness. In cases where there are some missing data, the patient will be asked those questions on the telephone (a member of the Investigator Team will call him/her).

It will be the responsibility of the Lead Researcher to ensure the accuracy of all data entered into the CRF. The delegation log will identify all those personnel with responsibilities for data collection and handling, including those who have access to the trial database.

